9.8 Quality control

The organization that is responsible for the conduct of the study (ZEG) has implemented different quality assurance procedures for day-to-day work. Internal audits confirm that ZEG fully complies with GPP ('Guidelines for Good Pharmacoepidemiology Practices' issued by the International Society for Pharmacoepidemiology in 2007), GEP (Good Epidemiological Practice issued by the European Epidemiology Federation in 2007), GVP (Good pharmacovigilance practices issued by the EMA in 2012/2013), the ENCePP Code of Conduct, the Nuremberg Code and the Declaration of Helsinki. Additionally, ZEG has been audited three times by large pharmaceutical companies, without major issues being identified. For this study, as for all other studies conducted by ZEG, site audits in the participating local field organizations will be conducted by ZEG on a regular basis. This includes organizational aspects as well as source data verification.

ZEG's internal standard operating procedures (SOPs) manual describes standardized working procedures to ensure high quality and compliance with all applicable guidelines. The SOPs are reviewed on an annual basis and updated where necessary to ensure that all processes are in line with legal compliance and integrity of data. ZEG also uses standardized working procedures for the Safety Monitoring and Advisory Council (SMAC), the Blinded Adjudication Board and study-specific working procedures for the local organizations.

ZEG assures that the study will be conducted in compliance with the protocol and any applicable regulatory requirements. All processes that are relevant for legal compliance of the study or the integrity of the data are subject to quality control measures. This includes 1) development of study protocol, questionnaires, databases and data entry screens, 2) data entry, 3) plausibility checks, 4) validation of clinical outcomes, 5) adverse outcome reporting, 6) data analysis, 7) report writing, 8) publication of results, 9) archiving of study materials (i.e. all baseline/follow-up questionnaires, other study documents and electronic files). All quality control measures are based on the four-eye principle (i.e., it is not sufficient that someone controls his/her own work). During study conduct the consistency between ZEG's electronic database and the original questionnaire will be audited several times by an external auditor.

The external auditor is also responsible for a systematic review of quality standards implemented at ZEG and the local organizations, as well as proposing suitable measures to ZEG management to improve quality standards.

ZEG's study work will be overseen for the whole study period by the Safety Monitoring and Advisory Council of internationally acknowledged experts in the field (cf. Section 10.3). This committee will take final decisions in all scientific matters.

9.9 Limitations of the research methods

In non-experimental studies like this prospective cohort study, the possibility of bias and residual confounding can never be entirely eliminated, and the ability to infer causation is correspondingly limited [8]. Valid information on potential sources of confounding and sophisticated statistical and epidemiologic methodology help to reduce the impact of bias and residual confounding [9]. However, the difficulty remains unresolved when all that exists is a weak association [10;11]. Relative risk estimates that are close to unity may not allow differentiation between causation, bias and confounding [12;13]. In general, it is difficult to interpret a relative risk of two or less in observational research [14;15].

Within these limitations of non-experimental studies the chosen study design is capable of minimizing bias and residual confounding. In our judgment, selection bias will not be a major issue in this study because study participants from several settings are included, e.g. private practices, family planning centers, hospitals. Although recruitment will be performed only by a sample of physicians, those can be considered the most possible representative network. In several countries where ZEG currently conducts similar observational studies, all possible recruiting physicians have been contacted and asked for participation. Furthermore, the participants' demographic characteristics have been proven to be representative for adult OC users in the EURAS-OC study, which had an almost identical study design. Differences between the study cohorts can be addressed in the statistical analysis (e.g. imbalances of age distribution will be levelled out by age adjustment to assure comparability of results).

Also, misclassification bias will probably have no substantial impact on the results as precise information on the exposure and the outcomes of interest will be available. In addition, reliable information on duration of current hormonal contraceptive use will be available. Accordingly, the study will capture the well-known increased VTE risk during the first months of combined hormonal contraceptive use [16;17;18]. Furthermore, the comprehensive follow-up procedures will ensure a low loss to follow-up rate. In theory, a disproportionately high percentage of SAEs (including VTE and ATE) could occur in those patients who are lost to follow-up, because SAEs could be the reason for the break in contact with the health care professional who prescribed their COC. An advantage of the study design, however, is that the investigator team will have direct contact with the participants; contact will not be lost if the women change health care professionals, for example (e.g., due to change of residence or dissatisfaction with treatment).

In contrast, it will be impossible to exclude diagnostic bias. Clinical symptoms of VTE cover the spectrum from a complete absence or unspecific, slight symptoms to dramatic, acute, life-threatening symptoms [19;20;21]. A high awareness of potential cardiovascular risks of combined oral contraceptive use may lead to more diagnostic procedures and, therefore, to more detected VTE. It is conceivable that this potential bias lead to an overestimate of the relative risk of a new product (such as FC Patch Low) cohorts compared to the LNG-cohort. Therefore, diagnostic bias should not result in an underestimate of the VTE risk carried by FC Patch Low.

Unlike in many other observational studies on hormonal contraceptives, a strength of the study will be the availability of information on many important prognostic factors for the outcomes of interest. Nevertheless, we acknowledge that due to the non-interventional character of the study, information on specific gene mutations will only be available for VTE cases but not for the vast majority of study participants who will not experience a VTE. This limitation will be mitigated through information on family history of VTE which has a higher predictive value for VTE compared to gene mutations [22].

This study combines several methodological strengths that are substantial for the validity of the results: i) prospective, comparative cohort design; ii) availability of important confounder information (e.g., BMI and family history of VTE); iii) validation of outcomes of interest and the exposure of the relevant cases; iv) comprehensive follow-up procedure and very low loss to follow-up to minimize underreporting; v) independent, blinded adjudication of VTE cases; vi) relevant statistical analyses (e.g., stratified analyses by user status and exposure period; comparison of isochronous, new user cohorts; sensitivity analyses on the impact of the adjudication process, outcome definition, and prognostic factor/covariate selection); vii) study population representative for oral contraceptive users under routine clinical conditions; viii) generalizability of results as hormonal contraceptive use in this study reflects routine clinical use and study participation is not limited by medical inclusion and exclusion criteria; ix) supervision by an independent Safety Monitoring and Advisory Council, and scientific independence from the study funder.

9.10 Other aspects

9.10.1 Validation of self-reported events

Under routine medical conditions, diagnosis of an SAE is not always confirmed by a diagnostic method with high specificity. Therefore, SAEs will be classified by the investigator team as “confirmed” or “not confirmed” according to the following predefined algorithm:

- **Definite Event:**

Confirmed by diagnostic measures with high specificity (e.g., phlebography for DVT, spiral CT for pulmonary embolism, cerebral MRT for cerebrovascular accidents, ECG with typical ST segment elevation for acute myocardial infarction, histology for gynecological cancer, two-sided blood pressure measurement with diastolic blood pressure of more than 120 mmHG for hypertensive crisis)

- **Probable Event:**

Absence of confirmation by a diagnostic measure with high specificity, but clinical diagnosis confirmed by a health professional or supported by diagnostic tests with low specificity (such as D-dimer for VTE or typical ECG/blood gas tests for PE). These cases are usually characterized by a subsequent specific therapy (such as fibrinolysis or long-term

anticoagulant therapy). However, if the attending physician confirms that the diagnosis is correct, the event will be classified as a probable event even if specific treatment was not given.

- Event not confirmed:
 - Diagnosis reported by the patient is excluded by diagnostic procedures
 - A different medical condition is diagnosed by the attending physician
 - The woman did not contact a health professional to clarify her symptoms and no diagnostic measures were performed that could have clarified the diagnosis

The exposure data reported by the patients will be validated via the prescribing physicians. Definite and probable events will be classified as ‘confirmed events’.

For VTE, the definition of “definite”, “probable” and “not confirmed” is further specified:

- **Definite VTE:** Confirmed by imaging procedure
 - DVT: phlebography, duplex sonography, magnetic resonance imaging
 - PE: pulmonary angiography, ventilation-perfusion scan, spiral computed tomography, magnetic resonance imaging, transesophageal echocardiography

- **Probable VTE:**

Absence of confirmation by an imaging test, but a clinical diagnosis was confirmed by a health professional or is supported by a non-imaging test (such as ultrasound doppler, plethysmography, D-dimer for VTE or typical ECG/blood gas tests for PE). These cases are usually characterized by a subsequent specific therapy (such as fibrinolysis or long-term anticoagulant therapy). However, if the attending physician confirmed that the diagnosis is correct, the event was classified as a VTE, even if a specific treatment was not given.

- **VTE not confirmed:**
 - VTE excluded by a physician
 - A different medical condition was diagnosed by the attending physician
 - Woman did not contact a health professional to clarify her symptoms and no diagnostic measures were performed that could have clarified the diagnosis

For the final analysis this classification will be verified by means of an independent blinded adjudication process (cf. Appendix 3).

For ATE, the definition of “definite”, “probable” and “not confirmed” is further specified as follows:

- **Definite ATE:** Confirmed by a diagnostic method with high specificity (incl. intraoperative or post-mortem)

- AMI: typical change of cardiac enzymes with high specificity (CK-MB, cardiac troponin, glycogen phosphorylase isoenzyme BB), typical ECG changes (e.g., ST-segment elevation), coronary angiography
- Stroke: typical clinical signs persisting for days, confirmation by imaging with high specificity (e.g., CT, MRI, cerebral angiography, PET)
- TIA: typical clinical signs (followed by resolution within 24 hours) and imaging with high specificity and sensitivity (e.g., MRI) does not indicate tissue necrosis
- Other organs and peripheral arteries (e.g. kidney, gut, adrenals, femoral artery): confirmed by imaging with high specificity (e.g., arteriography, CT, MRI)
- **Probable ATE**: No confirmation by a diagnostic method with high specificity, but other evidence pointing in the direction and the clinical diagnosis is confirmed by attending physician
 - AMI: typical clinical symptoms, change of cardiac enzymes with low specificity (e.g., CK, AST, LDH) or indirect ECG signs (e.g., ST-segment depression in case of posterior myocardial infarction), and clinical diagnosis confirmed by attending physician
 - Stroke: clinical signs persisting for days, confirmatory imaging not done or inconclusive, but clinical diagnosis confirmed by attending physician
 - TIA: typical clinical signs, followed by resolution within 24 hours, but no imaging with high specificity; and the clinical diagnosis is confirmed by attending physician
 - Other organs and peripheral arteries (e.g. kidney, gut, adrenals, femoral artery): confirmatory imaging not done or inconclusive, but clinical diagnosis confirmed by attending physician
- **ATE not confirmed**:
 - ATE excluded by a physician
 - A different medical condition was diagnosed by the attending physician
 - Woman did not contact a health professional to clarify her symptoms and no diagnostic measures were performed that could have clarified the diagnosis

9.10.2 Blinded adjudication

The following adjudication procedure will be established:

- 1) Independent adjudication by the individual specialists
- 2) Documentation of the individual assessments
- 3) Comparison of the individual assessments
- 4) Discussion of “split decisions” among the adjudicators without enforcement of a unanimous decision
- 5) Independent re-adjudication of the discussed cases by the individual adjudicators
- 6) Documentation of the individual post-discussion assessments

Based on this procedure six different classification strategies will be possible

- I. Classification of the reported event as confirmed if all adjudicators classify the event as confirmed before the discussion of “split decisions” took place (i.e., the decision is based on step 2 of the six-step procedure described above)
- II. Classification of the reported event as confirmed if all adjudicators classify the event as confirmed after discussion of “split decision” takes place (i.e., the decision is based on step 6 of the six-step procedure described above)
- III. Classification of the reported event according to the assessment of the majority of adjudicators before the discussion of “split decision” takes place (i.e., “majority vote” based on step 2 of the six-step procedure described above)
- IV. Classification of the reported event according to the assessment of the majority of adjudicators after discussion of “split decision” takes place (i.e., majority classification based on step 6 of the six step procedure described above)
- V. Classification of the reported event as confirmed if at least one adjudicator had classified the event as confirmed before the discussion of split decisions took place (i.e., “worst case decision” based on step 2 of the six-step procedure described above)
- VI. Classification of the reported event as confirmed if at least one adjudicator had classified the event as confirmed after the discussion of split decisions took place (i.e., “worst case decision” based on step 6 of the six-step procedure described above)

The final analysis will be based on strategy V (worst case decision without discussion of split decisions) because it represents the most conservative approach. Alternative analyses will be possible on request of the Safety Monitoring and Advisory Council or regulatory authorities.

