9.2.2 Selection of Study Population

Approximately 50,500 FC Patch Low users and 50,500 users of COC_{LNG} (including adolescents) will be recruited by participating physicians. Overall, 101,000 study participants are needed in order to provide approximately 150,000 woman-years (WY) (cf. Section 9.5), assuming a drop-out rate of approximately 0.7% per month.

Recruitment of study participants will be conducted via existing networks of contraceptive-prescribing health care professionals (e.g. gynecologists and general practitioners) who have participated in similar cohort studies in the past. Physicians will recruit FC Patch Low and

COC_{LNG} users in a 1 to 1 ratio. It is expected that this ratio reflects approximately the ratio of starter and restarter prescriptions of FC Patch Low and COC_{LNG} under routine clinical conditions. Only after the decision of the contraceptive prescription has taken place, the physician may ask the woman for study participation. For every FC Patch Low user recruited, the physician has to recruit the next new COC_{LNG} user (starter or restarter) who is willing to participate in the study.

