9.5 Study size

The sample size considerations are based on the expected VTE incidence for COC_{LNG} of 10 VTE per 10,000 WY²⁰, which was agreed upon recently with CHMP in a comparable PASS that is conducted by ZEG. It is expected that FC Patch Low is associated with a VTE risk that is not higher than the risk associated with COC_{LNG}.

The study should be powered to test non-inferiority of FC Patch Low treatment regarding VTE risk in comparison to COC_{LNG} use. Sample size calculations for a non-inferiority test of two exponential survival curves [6;7] showed that an expected number of 150 VTE cases should be sufficient to reach this goal. These calculations are based on the following assumptions: 1) one-sided α of 0.05; 2) power (1- β) of 0.80 and 3) non-inferiority limit on hazard ratio of 1.5.

At an incidence rate of 10.0/10,000 WY a total of 150 VTE cases could be expected within 150,000 WY. The drop-out rate in similar studies has been approximately 0.7% per month. Assuming 1) a recruitment phase of 60 months, 2) a follow-up phase of 12 - 24 months, and 3) a loss to follow-up rate of about 5%, follow-up of 101,000 study participants (50,500 FC Patch Low users and 50,500 COC_{LNG} users) for up to 24 months would result in approximately 150,000 WY (see table 1).

Based on these scenarios, the study is sufficiently powered to exclude a 1.5-fold VTE risk for FC Patch Low users compared to COC_{LNG} users in the event that the true VTE risk among FC Patch Low users is not higher than among COC_{LNG} users.

However, precise power calculations based on actual incidences and drop-out rates should be done on the basis of follow-up data 1) before the end of the recruitment phase and 2) after availability of 30,000 WY of observation. If these calculations do not confirm the assumed incidence and drop-out rates the Safety Monitoring and Advisory Council will discuss the need to decrease or increase the number of study participants and/or follow-up times.

The sample size needed for the investigation of the VTE risk is also sufficient for the evaluation of secondary outcomes – except ATE. Acute myocardial infarction and stroke are very rare in a female population of reproductive age. This study is powered to exclude a 2.5-fold risk of ATE. This is sufficient to screen for safety signals and substantial effects.

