9.7 Data analysis

Based on available data and pharmacological considerations the *a priori* assumption is that use of FC Patch Low is not associated with an increased risk of VTE compared to COC_{LNG}. That is, a statistical comparison of FC Patch Low and COC_{LNG} is not expected to show a difference. Therefore, a non-inferiority design was chosen to investigate the VTE risk of FC Patch Low. The primary analysis will be based on the comparison of the upper confidence limit for the point estimate of the VTE²² hazard ratio with the predefined non-inferiority limit (see below).

The final analyses will include both an “as treated” (AT) and an intention-to-treat (ITT) analysis using Cox regression models. The safety conclusions of the study, however, will be based on the AT analyses (outcomes of interest will be assigned to the treatment she used at the time of the event) because the ITT approach (outcomes of interest are assigned to the treatment which was prescribed at study entry) potentially dilutes differences between treatments.

Incidence rates, incidence rate ratios (HRs), excess risks, as well as crude and adjusted hazard ratios will be calculated. The appropriate confounding variables will be built into the model. Based on the expectation of a small absolute number of serious outcomes of interest the number of confounding variables will be limited to well-established risk factors for these outcomes (e.g., age, BMI, duration of current use, and VTE history). The final decision on the confounding variables will be made by the Safety Monitoring and Advisory Council before the first interim analysis of follow-up data. In addition, alternative analysis will be performed with other potential baseline risks to check the appropriateness of this decision. Similar analyses will be performed for all VTE (cf. Section 8) and arterial thromboembolism (e.g., acute myocardial infarction and stroke), the other secondary variables and other serious adverse events.

The null hypothesis to be tested is: $HR_{VTE} \geq 1.5$ (i.e., the VTE hazard ratio for FC Patch Low vs. COC_{LNG} is higher than or equal to 1.5). The alternative hypothesis is: $HR_{VTE} < 1.5$.

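### Adjudication strategy V is conservative for absolute VTE incidence but not for the non-inferiority test on the hazard ratio, and stricter rules are run only on request

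*Protocol*

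**What the plan says.** Section 9.10.2 of the protocol lists six ways to turn the adjudicators' votes into a classification: unanimous (I, II), majority (III, IV) and at least one positive vote (V, VI), each before or after split cases are discussed. It then chooses: "The final analysis will be based on strategy V (worst case decision without discussion of split decisions) because it represents the most conservative approach". On the other rules it says: "Alternative analyses will be possible on request of the Safety Monitoring and Advisory Council or regulatory authorities". Section 9.2.5 sets three adjudicators, blinded to the product used.

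Section 9.7 describes the primary analysis: "Therefore, a non-inferiority design was chosen to investigate the VTE risk of FC Patch Low". The upper confidence limit of the VTE hazard ratio is compared with 1.5, and the null hypothesis is a hazard ratio of 1.5 or more. The same section bases the safety conclusions on the as-treated analysis because intention-to-treat could dilute differences between treatments.

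Section 9.9 counts among the study's strengths "sensitivity analyses on the impact of the adjudication process, outcome definition, and prognostic factor/covariate selection", without naming the adjudication rules to be compared.

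**The concern.** Strategy V is the most inclusive of the six rules. Only split cases are discussed, so discussion can remove a case confirmed under V but cannot add one. Counting more events is cautious when the question is how many VTEs occur. The primary question is a ratio, and there caution runs the other way. False confirmations that arise equally in both cohorts carry a hazard ratio of 1, so they dilute a true excess, and the extra events narrow the interval.

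The protocol accepts this reasoning when it puts as-treated ahead of intention-to-treat, but does not apply it to adjudication. False reports are also to be expected: section 9.2.5 says that laypersons often misclassify events, and section 9.10.1 lets a VTE count as probable without imaging. At stake is the error rate of the study's one formal test, in the direction that favours the product.

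**Working it through.** **Inputs from the protocol**
- Design parameters (9.5): "one-sided α of 0.05; 2) power (1- β) of 0.80 and 3) non-inferiority limit on hazard ratio of 1.5".
- Events (9.5): the calculation "showed that an expected number of 150 VTE cases should be sufficient to reach this goal", and "At an incidence rate of 10.0/10,000 WY a total of 150 VTE cases could be expected within 150,000 WY".
- Cohorts recruited 1:1 (9.2.2), with 50,500 women each (9.5).

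**Input not in the protocol**
- f, the share of comparator events under strategy V that are false positives. This is an assumption, shown at 10%, 20% and 30%. The absolute false-positive rate is first taken as equal in both cohorts.

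**Step 1: the plan's own figure.** Schoenfeld's formula with equal allocation gives events = 4(1.645 + 0.842)² / (ln 1.5)² = 150.4. With 150 events and a true hazard ratio of 1, power is Φ(ln 1.5 × √150 / 2 − 1.645) = Φ(2.483 − 1.645) = 79.9%. The planned 150 events reproduce, so the sample size is not in question.

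**Step 2: hazard ratio estimated when the true value is 1.5.** Set the comparator's total event rate to 1. True events are 1 − f and false ones f. The patch rate is 1.5(1 − f) + f, which is also the estimated ratio.
- f = 10%: 1.35 + 0.10 = 1.45
- f = 20%: 1.20 + 0.20 = 1.40
- f = 30%: 1.05 + 0.30 = 1.35

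**Step 3: chance of falsely concluding non-inferiority.** With 150 events and p = HR/(1 + HR), it is Φ(ln(1.5/HR) × √(150 p(1 − p)) − 1.645).
- f = 0: Φ(−1.645) = 5.0%
- f = 10%: Φ(0.0339 × 6.02 − 1.645) = 7.5%
- f = 20%: Φ(0.0690 × 6.04 − 1.645) = 11.0%
- f = 30%: Φ(0.1054 × 6.06 − 1.645) = 15.7%

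**Step 4: cross-check with a different definition.** Keep 75 true comparator events, express false positives relative to those, and let them add to the total. The estimated ratio is (1.5 + f)/(1 + f), and false non-inferiority is 7.6%, 10.9% and 14.9% at 10%, 20% and 30%. Poisson simulation gave 7.9%, 11.2% and 15.1%. If the true ratio is 1, the estimate is unbiased, but the added events raise the pass rate from 79.9% to 83.1% (10%) or 85.9% (20%).

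**Step 5: unequal false-positive rates.** If the patch cohort's false-positive rate is k times the comparator's, the Step 2 ratio becomes 1.5(1 − f) + kf. It equals 1.5 for any f when k = 1.5. Under the Step 4 definition with f = 20%:
- k = 1.25: estimated ratio 1.458, false non-inferiority 7.5%
- k = 1.5: 1.500, 5.0%
- k = 2: 1.583, 2.0%

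**Step 6: power under a stricter rule.** If it confirms 10%, 20% or 30% fewer events, the Step 1 formula gives:
- 135 events: Φ(2.356 − 1.645) = 76%
- 120 events: Φ(2.221 − 1.645) = 72%
- 105 events: Φ(2.077 − 1.645) = 67%

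**The case against.** A reader might infer that the primary test's error rate does exceed 5%. The protocol does not support that. It gives neither an adjudicator error rate nor a frequency of split votes, so every f above is assumed. Blinding supports equal error per reported event, not per woman-year. Section 9.9 considers it conceivable that awareness leads to more diagnostic work-up with the new product. That passage concerns detected VTE, not false VTE, but more work-up could also bring more equivocal reports from patch users. By Step 5 this could offset or reverse the dilution. The objection stands as a limit on certainty. It does not rescue the rationale, because the offset is unquantified too.

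The figures also compare strategy V with an error-free rule. A majority rule admits some false positives, so the gap between V and majority is smaller than shown. This stands.

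A reader might also infer that strategy V must be abandoned for the hazard ratio. That goes too far. Split votes can be true VTE, particularly probable cases without imaging. Recovering them does not bias the ratio and adds valid events. The primary objective (section 8) also covers absolute risk, where V is the cautious choice. Step 6 shows what a stricter primary rule could cost in power.

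Finally, section 9.9 does foresee adjudication sensitivity analyses, and all individual votes are documented before and after discussion, so it would be wrong to say that nothing is planned. But 9.9 names no rule, and 9.10.2 leaves alternatives to a request. The two sections do not commit to the same thing.

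**Conclusion.** The point holds for the rationale and for the status of the alternative analyses. Calling strategy V the most conservative approach is right for absolute incidence and wrong, as a general reason, for a non-inferiority test on the hazard ratio. Confidence is high on direction, provided false positives occur at similar rates per woman-year in both cohorts. Confidence is low on size: about 7.5% to 16% false non-inferiority instead of 5% for assumed false-positive shares of 10% to 30%, measured against an error-free rule, and no inflation once the patch cohort's false-positive rate reaches about 1.5 times the comparator's. This should be fixed. It does not show that the primary test is invalid.

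**What to change.** In section 9.10.2:
- Limit the conservatism rationale for strategy V to absolute VTE incidence.
- Replace the on-request wording with mandatory, pre-specified hazard-ratio analyses under a majority rule (III or IV, named in advance) and the unanimous rule (I), and refer to these as the adjudication sensitivity analyses that section 9.9 lists.
- State that a non-inferiority conclusion under strategy V must be supported by the majority-rule result.
- State the assumption of similar false-positive rates, alongside the possible counter-bias described in section 9.9.

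Making the majority rule primary for the hazard ratio is an option, not a necessity.

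The cost is wording and a little more analysis, since the votes are already recorded. The stricter rules have less power (Step 6), so the plan should say beforehand what counts as support from the majority-rule result. All of this should be settled before adjudication begins, because choosing among six rules afterwards would be open to challenge.
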